Medifast® for Seniors Study October 16, 2015 NCT02730988 Study Title: Medifast® for Seniors Study

Principal Investigator: [name]

Co-investigator(s): [name], [name], and [name]

Sponsor or funding source: Jason Pharmaceuticals, Inc and the WFSM Older Americans Independence Center

Background, Rationale and Context

Aging and obesity are prevalent risk factors for morbidity and mortality. By 2030, Americans aged 65 and older will number an estimated 72 million people,¹ half of whom will be obese.² Both advanced age and obesity are well-characterized risk factors for chronic disease and disability,³ suggesting that the individual and societal health burden of age- and obesity-related conditions will increase substantially.

Intentional weight loss in obese, older adults remains controversial. Although caloric restriction, resulting in significant weight and fat mass loss, ameliorates many clinical consequences of obesity, recommendation of intentional weight loss in aging remains controversial.^{4,5} Reluctance stems, at least in part, from loss of lean and bone mass known to accompany overall weight loss,⁶ and potential exacerbation of age-related risk of disability⁷ and fracture.^{8,9} Accordingly, current treatment guidelines call for weight-loss therapy that minimizes muscle and bone losses for older persons who are obese and who have functional impairments or medical complications that can benefit from weight loss.¹⁰

Emerging results from randomized controlled trials demonstrate caloric restriction *and* exercise interventions, resulting in weight loss of 7-10%, are associated with initial improvement in muscle strength and function in older adults;¹¹⁻¹⁶ however, in few cases has the effect of caloric restriction, independent of exercise, been evaluated.^{13,16} and no randomized controlled trials have examined the role of specific dietary components, as adjuvants to weight loss, on physical function. Evidence supporting a diet-based weight loss approach in obese, older adults with functional impairments has tremendous clinical significance as multiple behavior changes are often difficult to implement and maintain, and many older adults are unable (or unwilling) to engage in the amount of physical activity typically prescribed in lifestyle-based interventions.

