Amount of dietary protein consumed during caloric restriction may be a key determinant in maintaining fatfree mass during weight loss. Adequate dietary protein is essential for skeletal muscle anabolism; and, epidemiological evidence in older adults point to a salutary effect of protein intake above the current RDA (0.8 g/kg/day) on body composition.^{17,18} Indeed, a recent position statement by the PRO-TAGE study group advises consumption of 1.0-1.2 g/kg/day in older adults *during weight-stable conditions* to aid in the maintenance of lean body mass and function.¹⁹ Practical achievement of this level of protein intake is often difficult for obese, older adults undergoing weight loss, yet may be critical to offset weight loss-associated lean mass loss. Preliminary data from our group show a lean mass sparing effect of high protein consumption during caloric restriction. In post-menopausal women undergoing a 5-month intentional weight loss program, consumption of a high (1.2 g/kg/day) versus low (0.6 g/kg/day) protein diet was associated with 50% attenuation (17% vs. 37%) of lean mass loss.²⁰ While promising, results have yet to be translated to functional changes in a tightly controlled trial of weight loss in obese, older adults.

The primary goal of this study is to determine whether adherence to a high protein (≥ 1.0 g/kg/d) weight loss program results in improved physical function by favorably affecting body composition compared to weight stability in obese, older adults. This will be accomplished by conducting a 24-week trial in 124 obese (BMI 30-42 kg/m²), older (65-79 years) men and women, at risk for mobility disability, randomized to either: (1) high protein intake (≥ 1.0 g/kg/d; n=62) during weight loss, or (2) weight-stable control (n=62).

Specific Aim 1: To compare the effects of high protein intake during weight loss versus weight stability on 24-week changes in physical function, primarily assessed by performance on the fast 400-meter walk test. *We hypothesize that participants randomized to a high protein weight loss intervention will experience greater improvements in 400-meter walk gait speed than participants who receive the weight-stable control condition.* **Specific Aim 2:** To compare the

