effects of high protein intake during weight loss versus weight stability on 24-week body composition changes (assessed by whole-body DXA). We hypothesize that participants randomized to a high protein weight loss intervention will present with a more favorable (i.e. higher) post-intervention lean to fat mass ratio compared to participants who receive the weight-stable control condition.

In exploratory analyses we will also examine the effects of intentional weight loss on a compilation of physiologic and biochemical markers (including: respiratory and kidney function, cognitive processing speed, inflammation, and blood pressure), shown in epidemiologic investigations to predict mortality.²¹ Meta-analytic data from our group suggest a 15% reduction in mortality for obese adults undergoing intentional weight loss,²² and better understanding of the potential mechanism(s) underlying this association is of great clinical interest.

Methods and Measures

Recruitment of study participants: We plan to recruit up to 124 obese (BMI=30-42 kg/m²), older (age=65-79 years) men and women with mobility disability from communities in and around Forsyth County, NC via media advertisements, mass mailings, and direct mailings. Based on our experience in recruitment of the designated population, we are confident in our ability to recruit older adults who meet the inclusion/exclusion criteria (see **Table 1**). We plan to recruit at a rate of 10-12 per month.

Inclusion Criteria	Exclusion Criteria		
Age 65-79 years	Weight loss or gain ($\pm 5\%$) in past 6 months		
BMI=30-42 kg/m ²	Prior bariatric surgery		
Confirmation of self-reported mobility disability, as assessed	Multiple food allergies		
by phone screen/clinical staff			
Self-reported sedentary behavior	Difficulty with hearing/vision that interferes with study participation		
Non-impaired cognitive function (MoCA>18)	Excessive alcohol use (>14 drinks/week)		
Stability of residence for next 2 years	Smoker (>1 cigarette/d within year)		
Willing and able to follow dietary protocol	Insulin-dependent or uncontrolled diabetes (FBG >140 mg/dl)		
Willing to provide informed consent	Uncontrolled hypertension (BP>160/100 mmHg)		
Approved for participation by study physician	Abnormal kidney tests (GFR<40, creatinine >2.0)		
Not involved in another behavioral or interventional research	Regular use of medications that may influence body weight or		
study	composition		

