BV1/ FV1	Fasting blood draw, snack, blood pressure, depression screen (CES-D), cognitive function (MoCA), waist circumference, cognitive processing speed (DSST), spirometry (FEV ₁), grip strength, leg muscle/power, instructions for accelerometry and 24-h urinary nitrogen test	X				Х	
BV2/ FV2	Muscle function tests (expanded SPPB, TUG, fast 20-m gait speed, fast 400-m walk test, stair climb) DXA (whole body, hip, spine), CHAMPS, SF-12, PAT-D, MAT-sf, dietary run-in instructions		Х				Х
RAND	Randomization			Х			
MP	DXA and fast 400 meter walk test (at 12-week visit, only)				Х		
INT	Bi-weekly adherence monitoring (weight, dietary trackers, meet with study dietitian as needed). Note: official pre/post intervention weights will be captured at weeks 0 and 24, respectively				Х		

Table 2. Proposed Assessment Timeline

Study Interventions

High Protein Weight Loss Group - Participants randomized to the high protein weight loss group will follow the Medifast 4 & 2 & 1 PlanTM, targeting ~10% weight loss over the 24-week study. Weight loss will be monitored bi-weekly to ensure the safety of the study participants. This level of weight loss will be achieved through a combination of meal replacement products (MRPs), meal plans, and individual nutrition/behavioral counseling. Participants will follow the Medifast 4 & 2 & 1 Plan which includes consumption of total of 4 Medifast MRPs per day, with the addition of 2 lean and green meals and 1 Healthy Snack. Medifast MRPs each contain ~90-110 kcals and 10-15 g protein. The lean and green meals will be prepared by the participants and each will consist of 5-7 oz. lean protein, 3 servings of non-starchy vegetables and up to 2 servings of healthy fat. The snack will consist of one serving of fruit, dairy, or grain. Participants will be guided by the study RD on their food purchasing and preparation of the other meals and will be encouraged to consume only what is approved from the menu.

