
- 3. Body composition. Dual Energy X-ray Absorptiometry (iDXA, GE Medical Systems, Madison, WI; located in the Health and Exercise Science Department, WFU). Whole body scans will be acquired with the participant supine and aligned with the scanner table as prescribed by the manufacturer. DXA will also be used to analyze bone mineral density (BMD) using specific scans of the anterior-posterior (AP) spine (L1-L4) and proximal femur. Coefficients of variation (CV) from repeated measurements are 1.0% for lumbar spine BMD and 1.0% for femur BMD. All scans will be performed and analyzed by our trained DXA technician who is certified by the International Society for Clinical Densitometry and has vast experience in body composition measurements in older adults. Every scan will be examined to evaluate for proper patient positioning and analysis, and reanalysis or rescanning will be performed if necessary. Any artifacts will be noted and, if possible, excluded from the measured region. Daily quality control scans are obtained with GE's phantoms. If results are more than 2 SD from baseline we repeat the phantom scan. If the results of both scans are more than 2 SDs from baseline we do not measure any more individuals and have the scanner serviced. Each week, the daily phantom data are analyzed to detect drifts. If changes in software or the machine occur, the scanner will be calibrated with the new software to ensure consistency.
- 4. Accelerometry will be used to objectively assess physical activity over a 7 day period at baseline and at follow-up. The ActiGraph wGT3X-BT is a compact, hip mounted electronic pedometer, using a 3-axis accelerometer and digital filtering algorithms to measure the amount and frequency of movement over 24 hours for up to 40 days. It provides physical activity measurements including raw acceleration, activity counts and vector magnitude, energy expenditure, steps taken, physical activity intensity, and body position.
- 5. Cognitive function. This will be assessed during screening using the **Montreal Cognitive Assessment** (MoCA), participants must score >18 to be eligible. We will also assess psychomotor speed, attention, and

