Data analyses: Regression diagnostics, residual plots, and exploratory analyses will be performed to find appropriate transformations for all variables to satisfy linearity, homogeneity of variances, and normality assumptions. Descriptive statistics consisting of frequency tables and percentages for categorical variables, and means, standard deviations, medians, and ranges for continuous variables will be tabulated and presented by intervention group and time point. Exact 95% confidence intervals (CIs) will be provided for the estimated proportions and approximate 95% CIs for estimated means. The primary outcome of the intervention effect on fast 400-meter walk gait speed will be analyzed using an ANCOVA model fit with the main effect of treatment arm and adjusted for baseline values of fast 400-meter walk gait speed. The primary test will be covariate-adjusted main treatment effect of the weight loss intervention compared to the control group, and we assume a Type I error rate of 0.05 for the two-sided alternative hypothesis. Secondary measures of body composition will be analyzed similarly, using baseline values of the particular body composition measure as a covariate in the outcome model. Other data including feasibility and compliance data collected in this study will be used to inform future studies of weight loss in older adults. All statistical analyses will be conducted assuming intent-to-treat so that participants will remain assigned to the initial randomization group regardless of treatment adherence, and participants who do not adhere or discontinue treatment will still be encouraged to provide outcomes data. Our group has past success in retaining participants by maintaining frequent contact with individuals who encounter barriers to participation and creatively accommodate and counsel, as necessary, to encourage the maximum degree of participation. To ensure the results are not overly influenced by missing data, a multiple imputation sensitivity analysis of the primary outcome will be performed using both baseline and post-randomization characteristics to inform the missing data imputation, assuming observations are missing at random.

Human Subjects Protection

Subject Recruitment Methods

We will recruit individuals using community-based recruitment strategies including mass and direct mailings and the local newspapers. We will also advertise in the VITAL newsletter (BG99-559) and participate in community outreach events.

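### Does Aim 2 need lean mass and fat mass named beside the lean-to-fat ratio?

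*Combined protocol and SAP*

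**What the plan says.** The Background gives the reason for caution about weight loss in older adults: "Reluctance stems, at least in part, from loss of lean and bone mass known to accompany overall weight loss". It then cites pilot data in which a high-protein diet, compared with a low-protein one, "was associated with 50% attenuation (17% vs. 37%) of lean mass loss". The text does not say what those percentages are percentages of. The primary goal is to learn whether the programme "results in improved physical function by favorably affecting body composition compared to weight stability in obese, older adults".

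Aim 2 compares high protein intake during weight loss with "weight stability on 24-week body composition changes (assessed by whole-body DXA"). Its one directional hypothesis is a "more favorable (i.e. higher) post-intervention lean to fat mass ratio compared to participants who receive the weight-stable control condition".

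Under Study Interventions, the weight loss arm follows a plan "targeting ~10% weight loss over the 24-week study", and controls are encouraged to stay within 5% of baseline weight. Under Study Measure(s), item 3 (Body composition), "Whole body scans will be acquired with the participant supine and aligned with the scanner table as prescribed by the manufacturer"; the same item adds bone density from separate spine and femur scans. Table 2 places DXA at baseline, week 12 and week 24, and official body weights at weeks 0 and 24.

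The Data analyses section says "Secondary measures of body composition will be analyzed similarly, using baseline values of the particular body composition measure as a covariate". The same paragraph provides means, standard deviations, medians and ranges of continuous variables by intervention group and time point, with approximate 95% confidence intervals for means. Lean mass and fat mass are not listed by name as Aim 2 outcomes.

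**The concern.** The protocol's worry is loss of lean tissue, but the quantity in its body composition hypothesis is a ratio that fat loss alone pushes up. Because the comparator does not lose weight, a higher ratio in the intervention arm is expected under good or poor lean sparing. The size of the effect is also ambiguous by itself, since it depends on how much weight was lost as well as on how much of that was lean.

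If the ratio were all that was reported, a significant result could be read as evidence that the programme protected lean mass when it had shown only that more fat than lean was lost. Lean and fat mass are not named, so one might also fear that the less favourable component could be left out after the data are seen.

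**Working it through.** **Inputs.** From the protocol: 10% target weight loss; 17% and 37% from the pilot data, read here as the lean share of weight lost, which is an assumption. Assumed, because the protocol gives no baseline composition: weight W = 95 kg, body fat 42% (range 35% to 55%), body weight as lean plus fat only, and controls unchanged. The protocol gives no figure of its own for the ratio, so there is none to reproduce.

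**When the ratio rises.** Let L and F be baseline lean and fat mass, D the kilograms lost and s the lean share of the loss. The ratio afterwards is (L − sD) / (F − (1 − s)D). It exceeds L/F exactly when s < L/(L + F). With 35% to 55% body fat, that threshold is 65% to 45%.

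**Central case.** L = 55.1 kg, F = 39.9 kg, ratio 55.1/39.9 = 1.381, D = 9.5 kg.

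| Lean share of loss | Lean lost (kg) | Ratio afterwards | Change |
|---|---|---|---|
| 17% | 0.17 × 9.5 = 1.62 | 53.49/32.02 = 1.671 | +21.0% |
| 37% | 0.37 × 9.5 = 3.52 | 51.59/33.92 = 1.521 | +10.1% |

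**Range of assumed body fat, 10% loss.**

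| Lean share of loss | 35% fat | 55% fat |
|---|---|---|
| 17% | +27.7% | +13.3% |
| 37% | +15.0% | +3.7% |
| 50% | +7.7% | −2.2% |

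The sign is positive for both pilot figures throughout. It is not guaranteed for every lean share.

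**Same ratio, different lean loss.** At 42% fat, a weight loss of 5.38% (5.12 kg) with a 17% lean share gives 54.23/35.65 = 1.521, again +10.1%, with only 0.87 kg of lean mass lost, against 3.52 kg in the second row of the first table. The ratio alone cannot tell these two apart.

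**Adding the measured weight.** Since lean plus fat equals weight in this model, L = weight × R/(1 + R), where R is the ratio.

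- 10% loss, R = 1.671: 85.5 × 1.671/2.671 = 53.49 kg lean.
- 10% loss, R = 1.521: 85.5 × 1.521/2.521 = 51.58 kg lean.
- 5.38% loss, R = 1.521: 89.88 × 1.521/2.521 = 54.23 kg lean.

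The ratio and weight together separate all three cases. For a single participant this is an identity of the two-part model. For group means it is approximate, because the mean of a ratio is not the ratio of means. In practice the step is not needed: the scan supplies lean and fat mass directly, and the ratio cannot be computed without them.

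**What the analysis text covers.** Aim 2 is framed as a comparison of body composition changes, and the ratio is one hypothesis within it. The analysis sentence is in the plural and adjusts for the baseline of the particular measure. That is a separate ANCOVA for each measure, which is what one would ask for lean mass and fat mass. Both are continuous variables, so the descriptive tables by group and time point also cover them.

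**The case for a change.** The strongest reply is that permitting an analysis is not the same as committing to it. The adjusted between-group difference in lean mass is nowhere promised by name, and an unnamed measure can be reported or left out once the results are known. The protocol itself makes lean loss a central concern and calls a higher ratio more favorable, so readers will want the components. Naming them would cost only wording.

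Part of this stands. The ratio's sign or significance must not be read as evidence of lean preservation, and the two components are not listed. But the protocol does not make that reading: its wording fixes the direction of the ratio and goes no further. A hypothesis about relative composition is a fair choice against weight-stable controls, because losing weight normally takes some lean mass with it, and a hypothesis of more lean mass than in controls would be a poor one. Function, strength and power, where lean loss would matter to participants, are measured directly. The general commitment to tabulate continuous variables by group and time point leaves little room for the components to go unreported.

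**Conclusion.** The algebra is right and the consequence is small. A higher ratio is compatible with about 1.6 kg or about 3.5 kg of lean mass lost at the targeted 10% weight loss, given an assumed 95 kg and 42% body fat and the pilot percentages read as lean share of weight lost. The protocol supplies none of those three assumptions and no standard deviation for the ratio, so nothing can be said about the chance of a significant result.

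No change is needed. Lean and fat mass are measured at every DXA visit, fall under the planned own-baseline ANCOVA and the planned descriptive tables, and can be read alongside recorded body weight. This is a gap in detail that an analyst following the plan fills in the ordinary course. The gait speed outcome, the sample size and data collection are not touched.

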- 8. Compliance and satisfaction: Although we will attempt to control compliance by the use of behavioral strategies, there may be inter-individual variability in compliance to the weight loss protocol. Therefore, participant weight will be collected at regular, bi-weekly intervals for both groups. Additionally, participants randomized to the high protein weight loss group also will be asked to provide information on daily dietary intake and complete a satisfaction survey at the end of intervention to express thoughts and feelings about following the Medifast 4 & 2 & 1 Plan. Lastly, 24-hour urine nitrogen will be assessed to ensure differential protein intake by sending participants home with a container and instructions at baseline and follow up. Participants will be asked to: (1) void at 8 AM and discard the specimen; (2) collect all urine including the final specimen voided at the end of the 24-hour collection period (i.e., 8 AM the next morning); (3) screw the lid on securely. The sample can be stored at room temperature or refrigerated for up to 14 days and when the sample is returned, it will be sent to Labcorp for analysis.

Statistical Analyses

Sample size: Unpublished data collected in older participants undergoing a 6-month weight loss intervention indicate that we can anticipate a clinically meaningful 400-meter walk gait speed difference of at least 0.05 m/s, with a common group standard deviation of 0.19 m/s and a correlation of 0.85 between baseline and 6-month measures. Using the method of Borm et al (2007),³⁴ we assume using an analysis of covariance (ANCOVA) analytic approach fitting the randomization effect and baseline gait speed, then 53 subjects completing the intervention per group will yield 80% power using a two-sided alternative hypothesis at the 0.05 level of significance. Assuming a conservative drop-out rate of 15%, we plan to enroll 124 participants (n=62/group).

Database management: To facilitate data transfer and preserve records that can be audited, we will use hard copy forms collection. All data will be manually entered within one week of collection into the study database. Our data entry system will protect confidentiality and data security and the use of text containing identifying information will be avoided. Data will reside on a server in a Microsoft SQL server database with daily backup.

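### The stated 80% power does not follow from the plan's own inputs: 53 completers per group give about 72%, and 80% needs 63 to 64 per group

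*Combined protocol and SAP*

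**What the plan says.** The sample-size paragraph (Statistical Analyses, Sample size) gives every input to the calculation:

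- Effect: "we can anticipate a clinically meaningful 400-meter walk gait speed difference of at least 0.05 m/s".
- Variability: "with a common group standard deviation of 0.19 m/s".
- Correlation: "a correlation of 0.85 between baseline and 6-month measures".
- Method: a published ANCOVA sample-size formula, cited as reference 34, with the model described as "we assume using an analysis of covariance (ANCOVA) analytic approach fitting the randomization effect and baseline gait speed".
- Result: "then 53 subjects completing the intervention per group will yield 80% power using a two-sided alternative hypothesis at the 0.05 level of significance".
- Enrolment: "Assuming a conservative drop-out rate of 15%, we plan to enroll 124 participants (n=62/group").

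The Data analyses paragraph specifies the same primary model (treatment arm plus baseline 400-metre gait speed) and again a two-sided test at 0.05. No other SD, correlation, effect, alpha or design adjustment appears in the document.

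**The concern.** With effect, SD, correlation, alpha, power and model all stated, the required number is fixed up to small differences between approximations. The number printed is 10 to 11 per group below it, which is too large a gap for the choice of approximation to explain.

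The calculation concerns the primary outcome of Specific Aim 1. The plan describes the 0.05 m/s difference as clinically meaningful, so a non-significant result would naturally be read as evidence against a meaningful effect from a trial with an 80% chance of finding one. If the true chance is nearer 72%, that reading is too strong.

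**Working it through.** **Inputs** (all from the sample-size paragraph): δ = 0.05 m/s, SD = 0.19 m/s, ρ = 0.85, two-sided α = 0.05, power 80%, 53 completers per group, 15% drop-out.

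**1. The plan's figure by its named method.** The method takes the two-sample size and multiplies it by (1 − ρ²).

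- Unadjusted size per group: 2(1.960 + 0.8416)² × 0.19² / 0.05² = 226.7.
- Design factor: 1 − 0.85² = 0.2775.
- Completers per group: 226.7 × 0.2775 = 62.9, so **63**.
- Starting instead from the t-based unadjusted size of 228: 228 × 0.2775 = 63.3, so **64**.

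The stated 53 is not reproduced.

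**2. Power at given numbers of completers.** The residual SD is 0.19 × √0.2775 = 0.1001. At n = 53 per group the standard error is 0.1001 × √(2/53) = 0.01944, and 0.05 / 0.01944 = 2.572. Normal-approximation power is Φ(2.572 − 1.960) = 0.730. The noncentral t uses 2n − 3 degrees of freedom (103 at n = 53).

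| Completers per group | Power, normal | Power, noncentral t |
|---|---|---|
| 53 | 73.0% | 72.2% |
| 62 | 79.4% | 78.8% |
| 63 | 80.1% | 79.4% |
| 64 | 80.7% | 80.1% |

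A simulation of the ANCOVA itself at 53 per group (20,000 runs) gave 71.9%. The result therefore does not depend on the cited formula.

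**3. Difference detectable with 80% power at 53 per group.** (1.960 + 0.8416) × 0.01944 = 0.0545 m/s by the normal approximation, and 0.0550 m/s by the noncentral t.

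**4. Enrolment implied by 80% power at 15% drop-out.** 63 / 0.85 = 74.1, so 75 per group. 64 / 0.85 = 75.3, so 76 per group. The total is 150 to 152, against the planned 124.

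**5. Other readings of the stated inputs.** Size per group for 80% power:

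| Reading | n per group |
|---|---|
| One-sided test at 0.05 | 50 |
| Change-score analysis | 69 (68.003 unrounded) |
| No baseline adjustment | 227 |
| 0.19 taken as the SD of change | 210 |
| Factor (1 − ρ) instead of (1 − ρ²) | 34 |
| Factor √(1 − ρ²) | 119.4, so 120 |
| Mean of the 12- and 24-week values (assuming ρ = 0.85 between them too) | 46 |

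None gives 53. The plan's two-sided, baseline-adjusted ANCOVA also rules out the first three.

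**6. What would give 53.** Changing one input at a time: δ of about 0.0545 m/s, SD of about 0.174 m/s, or ρ of about 0.875. Rounding of SD and ρ alone is not enough. At SD 0.185 and ρ 0.8549 the requirement is still 57.8 per group, and power at 53 is 76.5%.

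**7. The drop-out step.** 53 / 0.85 = 62.4, printed as 62, and 62 × 0.85 = 52.7. The step from 53 to 62 is consistent apart from rounding down. The full-sample requirement of 62.9 is also close to the 62 enrolled, so drop-out may have been subtracted from the required number instead of added to it. The document cannot confirm this, and the finding does not rest on it.

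**The case against.** The best defence is that the effect is worded as a lower bound and printed to two decimals. An unrounded value of 0.0545 m/s would meet that wording, round to 0.05 and give 53 with 80% power. Smaller joint shifts also work: 0.0525 m/s with SD 0.185 and ρ 0.8549 gives 52.5. This stands as a possible history of the number. It does not rescue the statement, because no such value is printed, and power claimed for a difference of at least 0.05 m/s has to hold at 0.05 m/s.

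A second point is that the 28% Type II error is conditional. It applies to a true difference of exactly 0.05 m/s and 53 analysed per group. The plan calls its 15% drop-out conservative and intends to collect outcomes from participants who stop the intervention, so the number analysed could lie anywhere from 53 to 62. That is fair, but power over that range runs from about 72% to 79% and does not reach 80% at the stated effect.

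Third, the discrepancy leaves Type I error, the analysis model and participant safety untouched, and moves the detectable difference only from 0.050 to about 0.055 m/s. A null result would also be judged by its confidence interval. This limits the practical damage but does not make the stated power correct.

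**Conclusion.** The concern holds. On the plan's printed inputs, 80% power needs 63 (normal) or 64 (noncentral t) completers per group, and the stated 53 give 73.0% or 72.2%. The shortfall is 10 to 11 completers per group and 7 to 8 percentage points of power. Enrolling 62 per group would not quite reach 80% even with no drop-out.

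These figures take the inputs as printed, with a true difference of exactly 0.05 m/s, equal groups, a common SD and the stated two-sided ANCOVA. The document does not show whether the 53 or one of the inputs is in error. Either way the paragraph contradicts itself on the primary outcome and must be corrected.

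**What to change.** Take one of two routes, depending on what the original calculation used.

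- **If the inputs are right**, restate the result along these lines: *With 53 completers per group (62 enrolled, 15% drop-out), the ANCOVA has about 72% power to detect 0.05 m/s, or 80% power to detect about 0.055 m/s, at two-sided 0.05.*
- **If an input was mistyped or over-rounded**, print the value actually used, with its source and enough decimals for a reader to reproduce 53.

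The input should not be chosen after the fact to make 53 come out. The cost is protocol wording and a less favourable stated power; no extra participants are needed. Only keeping 80% power at 0.05 m/s on the present inputs would require more enrolment, at 75 to 76 per group.
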